4.6.3. Laboratory Data

Clinical laboratory values will be expressed in SI units.

Summary data for each laboratory parameter will be presented for each continuous clinical laboratory parameter (including hematology, serum chemistry, coagulation studies and thyroid and liver function tests). Descriptive statistics will be presented for the actual values, change, and percentage change from baseline by visit.

For each continuous laboratory parameter, results will be categorized as low, normal, or high based on the laboratory normal ranges. Shift tables will be employed to summarize the baseline category versus the post-baseline category, where the post-baseline category will be based on the maximum difference (in absolute value) from the upper or lower limit of the normal range. All out-of-range and clinically significant laboratory results will be identified in subject data listings.

A listing will be produced for all subjects with abnormal liver function tests defined as an ALT $>3\times\text{ULN}$, AST $>3\times\text{ULN}$, and/or total bilirubin $>2\times\text{ULN}$ at any time point.

A table will be produced to summarize the number and percentage of subjects in each of below category at any post-baseline time point. ALT $>1 \text{ & } \leq 3$, $>3 \text{ & } \leq 5$, $>5 \text{ & } \leq 10$, $>10 \text{ & } \leq 20$, $>20 \times \text{ULN}$,

- AST $>1 \text{ & } \leq 3$, $>3 \text{ & } \leq 5$, $>5 \text{ & } \leq 10$, $>10 \text{ & } \leq 20$, $>20 \times \text{ULN}$,
- ALT or AST $>1 \text{ & } \leq 3$, $>3 \text{ & } \leq 5$, $>5 \text{ & } \leq 10$, $>10 \text{ & } \leq 20$, $>20 \times \text{ULN}$,
- ALP $> 1.5 \times \text{ULN}$,
- Total Bilirubin $>1.5 \text{ & } \leq 2$, $>2 \text{ & } \leq 3$, $>3 \text{ & } \leq 5$ and $>5 \times \text{ULN}$,
- Total Bilirubin $> 2 \times \text{ULN}$ concurrent with ALT or AST $> 3 \times \text{ULN}$.

A shift table from baseline to worst post-baseline for ALT, AST, and total bilirubin will also be provided.

For hematology and blood chemistry, summary tables of potentially clinically significant abnormalities will be provided. The results may also be graded according to the NCI CTCAE Version 4.0 or above. A shift summary of baseline to maximum post-baseline CTCAE grade may be presented, as appropriate.

The estimated glomerular filtration rate (eGFR, mL/min/1.73 m²) will be categorized as below: ≥ 90 ; 60-89; 30-59; 15-29 and <15 . A shift summary of baseline to worst post-baseline eGFR category will be presented.

All laboratory data will be provided in data listings. Laboratory values outside of the normal ranges will be listed separately, together with comments as to their clinical significance.

4.6.4. Vital Signs and Physical Examination

Descriptive statistics will be provided for vital signs, including blood pressure, pulse rate, oral body temperature and respiration rate. Summaries will also include change from baseline at each scheduled visit.

Vital sign measurements will be presented for each subject in a data listing.

Abnormal physical examination findings will be presented in by-subject data listing.

4.6.5. Electrocardiogram

Electrocardiogram (ECG) findings will include rhythm, ventricular rate, PR interval, QRS duration, QT interval, and QTc interval. Descriptive statistics will be provided for each measure over time. Change from pre-dose to each post-dose assessment will also be summarized.

Corrected QT interval (QTc) will be calculated using both Fridericia's and Bazett's correction formula. Categorical analyses of the QTcF/QTcB data will be conducted and summarized as follows:

- The number and percentage of subjects with maximum increase from baseline in QTcF/QTcB (<30, 30-60, >60ms)
- The number and percentage of subjects with maximum post-baseline QTcF/QTcB (<450, 450-< 480, 480-500, >500ms)

A listing will be provided for subjects with any post-baseline value > 500ms or an increase > 60ms.

All ECG data for each subject will be provided in a data listing.

4.6.6. Premedication

All patients received premedication in order to reduce the potential of an IRR. The original premedication regimen as outlined below was used at the start of the study. A subset of patients experienced AEs suspected to be related to steroids (eg, flushing) and were transitioned to a modified premedication regimen, with a reduced dose of corticosteroid to mitigate these events, as sanctioned in the protocol. After observing that the subset of patients tolerated the lower corticosteroid dose with no increase in IRRs, the protocol was amended (Global Amendment 1) to transition the rest of the patients to the modified premedication regimen (see below).

The following original premedication regimen was used prior to Global Amendment 1:

- Dexamethasone 8 mg PO or equivalent administered the evening before dosing and 20 mg PO at least 60 minutes prior to the start of the infusion of patisiran;
- Paracetamol 500 mg PO or equivalent administered the evening before dosing and at least 60 minutes prior to the start of the infusion of patisiran;
- H2 blocker PO (e.g., ranitidine 150 mg or famotidine 20 mg or equivalent other H2 blocker dose) administered the evening before dosing and at least 60 minutes prior to start of the infusion of patisiran; and
- H1 blocker PO, 10 mg cetirizine or equivalent (hydroxyzine 25 mg or fexofenadine could be substituted if patient did not tolerate cetirizine) administered the evening before dosing and at least 60 minutes prior to start of the infusion of patisiran.

The following modified premedication regimen was instituted with Global Amendment 1:

- Dexamethasone 10 mg IV or equivalent, administered at least 60 minutes prior to the start of the infusion of patisiran;
- Paracetamol 500 mg PO or equivalent at least 60 minutes prior to the start of the infusion of patisiran;
- H2 blocker IV (e.g., ranitidine 50 mg, famotidine 20 mg, or equivalent other H2 blocker dose) at least 60 minutes prior to the start of the infusion of patisiran; and
- H1 blocker IV, diphenhydramine 50 mg (or equivalent other IV H1 blocker available at the study site) at least 60 minutes prior to the start of the infusion of patisiran. Hydroxyzine

25 mg PO or fexofenadine 30 or 60 mg PO or cetirizine 10 mg PO could be substituted for any patient who did not tolerate IV diphenhydramine or other IV H1 blocker.

A drug exposure table summarizing the treatment duration under “original” and “modified” regimens will be provided. A patient who switches from “original” to “modified” regimen during treatment will be counted in both categories. TTR percentage reduction, AE/IRR incidence rates will also be summarized by original and modified regimens of premedication.

Premedication data will be listed. In addition, a listing for patients with premedication regimen change during treatment will be provided to display the study day of regimen change and durations of study drug exposure under original and modified regimens.

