4.6.2. Adverse Events

All AEs will be coded using the MedDRA coding system and displayed in tables and data listings using system organ class (SOC) and preferred term.

Analyses of AEs will be performed for those events that are considered treatment-emergent, where treatment-emergent is defined per protocol as any AE with onset during or after the administration of study medication through 28 days following the last dose of study drug. In addition, any event that was present at baseline but worsened in intensity or was subsequently considered drug-related by the Investigator through the end of the study will be considered treatment-emergent. Events with a fully or partially missing onset date will be assumed to be treatment emergent unless it can be unequivocally determined (from the partial onset date and/or a partial or complete stop date) that the event occurred prior to the first administration of study medication.

AEs are summarized by the numbers and percentages of subjects reporting a given AE. Therefore, in any tabulation, a subject contributes only once to the count for a given AE (overall, by SOC, by preferred term).

Tabulations by SOC and preferred term will be produced for all AEs, for all AEs related to study medication, for all severe AEs, for all AEs leading to study discontinuation, and for all serious AEs. Separate summary tables will be provided characterizing signs and symptoms of IRRs and AEs related to pre-medications. The incidence and frequency of IRRs over time will also be provided. AEs and serious AEs will be also summarized for Cardiac Subgroup. AEs will be tabulated by preferred term in decreasing order in frequency.

Separate tables will present AE incidence by maximum relationship to study drug and by maximum severity. Subjects who report multiple occurrences of the same AE (preferred term) will be classified according to the most related or most severe occurrence, respectively.

No formal hypothesis-testing analysis of AE incidence will be performed.

All AEs occurring on-study will be listed in subject data listings. A separate listing will be provided for IRRs. Listings will be provided for any AEs caused by pre-medications or any study procedure.

By-subject listings will also be provided for the following: subject deaths, SAEs, and AEs leading to discontinuation.

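### SAP 4.6.6 sets AE and IRR incidence side by side for two premedication regimens with no denominator or attribution rule; under the SAP's default counting, unequal infusion numbers and order can distort the comparison

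*SAP*

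**What the plan says.** SAP Section 4.6.6 defines an original and a modified premedication regimen and states that "TTR percentage reduction, AE/IRR incidence rates will also be summarized by original and modified regimens of premedication". No denominator is given, and nothing says to which regimen an event belongs.

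On switchers, the same section says: "A patient who switches from “original” to “modified” regimen during treatment will be counted in both categories". That sentence directly follows the one on the exposure table; the AE/IRR sentence comes next and uses the same two categories.

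The general counting rule is in SAP Section 4.6.2: "AEs are summarized by the numbers and percentages of subjects reporting a given AE". It continues: "Therefore, in any tabulation, a subject contributes only once to the count for a given AE (overall, by SOC, by preferred term".

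On sequence, Section 4.6.6 says "The original premedication regimen as outlined below was used at the start of the study". Some patients with suspected steroid-related AEs then moved to the modified regimen, and Global Amendment 1 moved the rest.

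Related outputs are also planned: treatment duration by regimen and a listing of each regimen change with its study day and the exposure on either side (Section 4.6.6), a separate IRR listing, and "The incidence and frequency of IRRs over time will also be provided" (Section 4.6.2).

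**The concern.** If the Section 4.6.2 rule is applied, the table shows, for each regimen, the percentage of patients with at least one event while on it. Three features make that percentage a poor measure of regimen risk.

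- **Exposure.** A patient with more infusions under one regimen has more chances to enter that regimen's numerator. Counting a switcher in both groups equalises the patients but not the infusions.
- **Order.** For every switcher the original regimen precedes the modified one. Any change in risk over successive infusions is read as a regimen effect.
- **Selection.** Early switchers had a suspected steroid-related AE before they switched. If events are placed by onset, each of them puts an AE in the original column by construction. This affects the AE comparison directly and the IRR comparison less clearly.

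Safety of long-term dosing is the primary objective, and premedication is given to reduce IRRs. A reader will use this table to ask whether lowering the steroid dose changed IRR frequency, and could draw the wrong conclusion in either direction.

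**Working it through.** The plan states no IRR rate, no infusion count by regimen and no power figure for this comparison, so there is no figure of the plan's own to reproduce. The check is how far the default percentage can move when the regimens do not differ.

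**Inputs from the documents.** Dosing is every 21 days from Day 0, with the last scheduled dose on Day 735 (schedules of assessments, both documents): 735/21 + 1 = 36 infusions. Up to 28 patients (SAP Section 3.1).

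**Assumptions, not from the documents.** Per-infusion IRR risk p, the same under both regimens, constant, and independent between infusions and patients; k infusions under the original regimen and 36 − k under the modified one.

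**Formula.** P(at least one IRR in k infusions) = 1 − (1 − p)^k. For p = 2%, k = 6: 1 − 0.98^6 = 11.4%; for the other 30 infusions, 1 − 0.98^30 = 45.5%.

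Percentage of patients with an IRR, original vs modified, no regimen effect:

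| Split | p = 1% | p = 2% | p = 5% |
|---|---|---|---|
| 6/30 | 5.9 vs 26.0 | 11.4 vs 45.5 | 26.5 vs 78.5 |
| 12/24 | 11.4 vs 21.4 | 21.5 vs 38.4 | 46.0 vs 70.8 |
| 18/18 | 16.5 vs 16.5 | 30.5 vs 30.5 | 60.3 vs 60.3 |
| 24/12 | 21.4 vs 11.4 | 38.4 vs 21.5 | 70.8 vs 46.0 |
| 30/6 | 26.0 vs 5.9 | 45.5 vs 11.4 | 78.5 vs 26.5 |

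In 28 patients, the 6/30 split at 2% means an expected 3.2 against 12.7 patients. Over p from 0.5% to 5% and these splits, the spurious original/modified ratio runs from 0.21 to 4.7. It is 1.00 at 18/18.

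**Reversing a real difference.** If the modified regimen halved the risk from 2% to 1%, a 6/30 split would show 1 − 0.98^6 = 11.4% against 1 − 0.99^30 = 26.0%.

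**Hiding a real difference.** If it doubled the risk from 2% to 4%, a 24/12 split would show 1 − 0.98^24 = 38.4% against 1 − 0.96^12 = 38.7%.

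**Order alone.** Let the risk at infusion j be p_j = 0.05·exp(−0.05(j − 1)), with no regimen effect. The percentage of patients is 1 − Π(1 − p_j) over the infusions under each regimen. At 18/18 this gives 46.2% against 22.1%, so an equal split does not protect against order.

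**What a per-infusion rate repairs.** With constant risk, IRRs divided by infusions give a ratio of 1.00 at every split. With the declining risk above they do not: at 12/24 the mean risks are 3.85 and 1.64 per 100 infusions, a ratio of 2.35 with no regimen effect. With first-infusion risk of 5% to 10%, decline rates of 0.05 to 0.10 and splits from 6/30 to 24/12, that ratio runs from about 2.3 to 7.2. The rate removes the exposure artefact and leaves the order effect.

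**The case against.** The strongest reply is that Section 4.6.6 speaks of incidence rates without saying percent of patients, and that its sentence on switchers belongs to the exposure table. Both readings of the wording are fair. A reader might infer that the SAP prescribes per-patient counting with double entry for this table; it does not say so. But Section 4.6.2 applies its rule to any tabulation, and no other rule is offered, so a programmer following the SAP would most likely produce percentages of patients.

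A reader might also infer that unequal infusion numbers will decide the result. The documents do not support that: no split is given, and at 18/18 with constant risk the artefact vanishes. If IRRs cluster in a few patients, the percentages also rise less steeply with infusion number than the table shows.

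It is also fair that the study is small and descriptive, with no hypothesis tests (SAP Section 3.2), and that the duration table, regimen-change listing, IRR listing and IRR frequency over time let a careful reader place events before or after each switch. These outputs give context. They adjust no percentage, and the frequency over time is not stated to be by regimen or per infusion.

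Finally, it would go too far to call this table the only evidence on the lower steroid dose or the basis for adopting it. Section 4.6.6 reports that the amendment came "After observing that the subset of patients tolerated the lower corticosteroid dose with no increase in IRRs", so the change preceded this analysis.

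**Conclusion.** The concern holds in a limited form. Section 4.6.6 leaves the denominator and the attribution of events open. Under the SAP's default counting, unequal infusion numbers and fixed order can create, reverse or hide a difference between regimens, and selection of early switchers can add to the original regimen's AE count.

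The size cannot be known from the documents. With equal 2% risk it ranges from nothing at 18/18 to 11.4% against 45.5% at 6/30, with the direction depending on which regimen has more infusions. These figures rest on an assumed split and on constant, independent risk; the order figures rest on an assumed decline. The inference that the default rule applies to this table is reasonable but not certain.

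It would be a mistake to conclude that a per-infusion rate makes the comparison causal. Regimen, order and selection remain partly inseparable in this design. The point is worth correcting in the SAP, but it concerns one descriptive safety summary and not the study's safety conclusions as a whole.

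**What to change.** In SAP Section 4.6.6:

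- Assign each AE and IRR to the regimen in force at its onset.
- Report IRRs per 100 infusions and AEs per patient-month under each regimen, next to the percentage of patients and with the denominators shown. Section 4.6.1 already defines a month as 30.44 days.
- Show IRRs per infusion by infusion number, and before versus after the switch in patients who received both regimens.
- State how premedication steroid doses outside the two defined regimens are classified. Protocol Section 5.5 allows step-down after steroid intolerance and Section 5.11 allows step-up after an IRR, so these changes depend on the events being counted.
- Label the comparison descriptive, non-randomised and sequential, and note that order and selection cannot be fully separated from regimen.

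The cost is SAP wording and some added table rows. Dosing, premedication and regimen-change data are already planned for listing, so no new data are needed. The downside is sparse counts in up to 28 patients, above all by infusion number; broad bands or a simple plot would limit this.

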4.6.7. Concomitant Medications

Concomitant medications will be coded using the WHO Drug Dictionary. Results will be tabulated by anatomic therapeutic class (ATC) and preferred term. Medications taken as protocol specified pre-medications will be summarized separately.

For concomitant medications, any medications that did not end prior to first dose will be included. If an end date is missing or the medication is ongoing, the medication will be included.

The use of concomitant medications will be included in a by-subject data listing.

4.6.8. Ophthalmology Examinations

Ophthalmology examinations include Visual Acuity, Slit Lamp Biomicroscopy, Intraocular Pressure, Dilated Indirect Ophthalmoscopy, and Fundus Photography.

Visual Acuity Exam and Intraocular Pressure Results: The actual value and change from baseline results will be summarized.

Biomicroscopy (Slit Lamp) and Dilated Indirect Ophthalmoscopy Exam Results: For the baseline results, the number and percentage of patients falling into each category of the examination status (normal, abnormal/not clinically significant, abnormal/clinically significant) will be summarized for each eye structure. For post-baseline results, the number and percentage of patients falling into each category of the examination status (new findings/worsening of finding, no change, improvement of finding etc) will be summarized for each eye structure.

Abnormal fundus findings at baseline will be recorded in the medical history log. Treatment-emergent abnormal fundus findings that are considered clinically significant will be recorded in the adverse event log.

Data for each of these assessments will be provided in a data listing.

4.6.9. Suicide Questionnaire

Data from the C-SSRS questionnaire will be provided in a data listing.

4.7. Measures of Cardiac Structure and Function

For those patients in the Cardiac subgroup, cardiac structure and function will be assessed through echocardiograms as well as measurement of serum levels of the cardiac biomarkers NT-proBNP and troponin I. Quantification of these biomarkers will be performed at a central

laboratory. The assessments will be conducted prior to the first dose of study drug and approximately once every 3 months.

Descriptive statistics will be provided for actual values, changes, and percentage changes from baseline in echocardiogram parameters (including wall thickness, LV strain and other Echo parameters), serum levels of troponin I and NT-proBNP.

All echocardiogram and cardiac function biomarkers data will be presented in patient data listings.

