Premedication Administration ^s			X	X	X	X	X	X	X	X	X		
Study Drug Administration ^t			X	X	X	X	X	X	X	X	X		
Plasma PK Sampling ^u			X ^v	X ^v	X ^v	X ^v	X				X	X ^w	
Urine PK Sampling ^x			X ^v	X ^v	X ^v	X ^v	X				X	X ^w	

Procedure	Visit Type	Screening/ Baseline ^a	Dosing										Mid- year/Annual Efficacy Assessment
			1 & 28	4 & 31	7 & 34	10 & 37	13 & 40	16 & 43	19 & 46	22 & 49	25 & 52	27 & 54	
	Study Week	NA											
	Study Day	Day -28 to -0	D0 & D189	D21 & D210	D42 & D231	D63 & D252	D84 & D273	D105 & D294	D126 & D315	D147 & D336	D168 & D357	D182 & D371	
	Window	NA	±3D ^b	±3D	±3D	±3D	±3D	±3D	±3D	±3D	±3D	±3D	±5D
PK/PD Subgroup Only													
TTR (ELISA and turbidimetric) ^y			X		X								
RBP and Vitamin A ^y			X		X								
Plasma PK Sampling			X ^z		X ^z								
Urine PK Sampling			X ^{aa}		X ^{aa}								
Cardiac Subgroup Only:													
Echocardiogram													X
Troponin I and NT-proBNP			X ^d					X				X	
Concomitant Medications		X						X					
Adverse Events								X ^{bb}					

Note: The schedule of assessments for patients administered ALN-TTR02 once every 4 weeks is provided in Appendix 2.

- a Assessments performed during the ALN-TTR02-002 study that occur within the Screening/Baseline timeframe will not need to be repeated at the Screening/Baseline visit.
- b Window does not apply to Day 0.
- c Any AEs from the previous study (ALN-TTR02-002) that are ongoing on Day 0 are to be recorded on the Medical History case report form for the current study (ALN-TTR02-003) and followed until resolution.
- d To be performed only on Day 0, not on Day 189.
- e On dosing days, weight will be measured predose.
- f On dosing days, vital signs will be measured predose. Vital signs to include: blood pressure, pulse rate, oral body temperature, and respiratory rate. Parameters are to be measured in the supine position using an automated instrument after the patient has rested comfortably for 10 minutes.
- g Triplicate recordings will be obtained.
- h A pregnancy test will be performed on all females of child-bearing potential at Screening/Baseline and any time pregnancy is suspected.
- i To be performed before administration of premedications and dosing with ALN-TTR02.

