4.2 Inclusion Criteria

Each patient must meet all of the following criteria within the Screening/Baseline period to be enrolled in the study:

1. Patients have previously received and tolerated ALN-TTR02 in Study ALN-TTR02-002.
2. Karnofsky performance status of 60% or greater.
3. Absolute neutrophil count (ANC) ≥ 1500 cells/mm³, platelet count $\geq 100,000$ cells/mm³, and hemoglobin ≥ 10 g/dL.
4. Adequate liver function, demonstrated by an aspartate transaminase (AST) and alanine transaminase (ALT) levels $\leq 2.5 \times$ the upper limit of normal (ULN), total bilirubin level within normal limits, albumin >3 g/dL, international normalized ratio (INR) ≤ 1.2 .
5. Adequate renal function, demonstrated by serum creatinine level $\leq 1.5 \times$ ULN.
6. Women of child-bearing potential must have a negative pregnancy test, cannot be breast feeding, and must be using 2 highly effective methods of contraception prior to screening, throughout study participation, and for 75 days after the last dose of study medication. Highly effective methods of birth control are defined as: hormonal - oral, implantable, injectable, or transdermal contraceptives in conjunction with spermicide, condom, or diaphragm; mechanical - spermicide in conjunction with a barrier such as a condom or diaphragm; intrauterine device in conjunction with spermicide or condom; or surgical sterilization of partner in conjunction with spermicide, condom, or diaphragm.
7. Males agree to use appropriate contraception throughout study participation and for 75 days after the last dose of study medication.
8. Patient is willing and able to comply with protocol-required visit schedule and visit requirements and provide written informed consent.

Additional inclusion criteria for patients participating in the PK/PD subgroup include:

9. At the time of enrollment, at least 6 months have elapsed since the patient's last dose of ALN-TTR02.

Additional inclusion criteria for patients participating in the Cardiac subgroup:

10. Have a left ventricular wall thickness of ≥ 13 mm on transthoracic echocardiogram.

11. Be normotensive or have hypertension that is well-controlled.
12. Absence of aortic valve disease.

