6.2.4 Additional Assessments for Cardiac Subgroup

For patients who are eligible for inclusion in the Cardiac subgroup:

- Perform an echocardiogram at the Mid-year and Annual study visits.

- Collect blood sample for assessment of NT-proBNP and troponin I at first dose and approximately once every 3 months.

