7.6.14 Echocardiogram

An echocardiogram will be performed in all patients at Screening/Baseline, to assess any cardiac abnormalities. In addition, for those patients enrolled in the Cardiac subgroup, an echocardiogram will be performed during approximately once every 6 months.

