3.4. Baseline Definitions

Unless otherwise noted, baseline will be defined as the study ALN-TTR02-003 Day 1 pre-dose value when non-missing, otherwise the latest value from amongst any screening or unscheduled assessments prior to dosing on Day 1 will be used (i.e., the measurement closest to and prior to dosing will be considered baseline). For PD parameters (TTR, RBP, vitamin A), baseline will be defined as the average of all records, including those from any unscheduled visits, prior to the date and time of first dose. For the mNIS+7/NIS+7 total score and individual components, grip test and 10m walk test, baseline is defined as the average of the Screening/Baseline assessments.

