3.7. Subpopulations

Patients who have pre-existing cardiac amyloid involvement will be eligible for inclusion in the cardiac subgroup for analysis. The inclusion criteria are the following:

- 1) Have a left ventricular wall thickness of ≥ 13 mm on transthoracic echocardiogram;
- 2) Be normotensive or have hypertension that is well-controlled;
- 3) No aortic valve disease.

Patients enrolled in the cardiac subgroup will complete additional clinical activity assessments to evaluate cardiac structure/function. This will be achieved through echocardiograms and monitoring of NT-proBNP and troponin I.

Patients will be eligible for inclusion in the PK/PD subgroup if their last dose of patisiran was administered at least 6 months prior to the first dose in this study. Patients enrolled in the PK/PD subgroup will have additional samples taken for evaluation of PK and PD (TTR and secondary PD biomarkers [RBP and vitamin A]).

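### The echocardiogram that selects the Cardiac subgroup at 13 mm is also its baseline for wall thickness, so mean change is biased toward apparent thinning

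*SAP*

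**What the plan says.** **Selection.** SAP 3.7 and Protocol 4.2 (criterion 10) define the Cardiac subgroup by the same cut-off: "Have a left ventricular wall thickness of ≥ 13 mm on transthoracic echocardiogram". Blood pressure and aortic valve conditions also apply. Protocol 4.2 fixes the time at which criteria are judged: "Each patient must meet all of the following criteria within the Screening/Baseline period to be enrolled in the study".

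**Pre-dose imaging.** Protocol 7.6.14 states: "An echocardiogram will be performed in all patients at Screening/Baseline, to assess any cardiac abnormalities". The schedule has no echocardiogram on the first dosing day. A parent-study echocardiogram inside the window stands in for the screening one and does not add a second reading (Protocol Table 1-1, note a): "Assessments performed during the ALN-TTR02-002 study that occur within the Screening/Baseline timeframe will not need to be repeated at the Screening/Baseline visit".

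**Follow-up imaging.** For the Cardiac subgroup only, Protocol 6.2.4 says: "Perform an echocardiogram at the Mid-year and Annual study visits".

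**Baseline.** SAP 3.4 uses the Day 1 pre-dose value if there is one and otherwise the latest earlier value, in short: "the measurement closest to and prior to dosing will be considered baseline". Averaged baselines are reserved for the PD parameters, mNIS+7/NIS+7, grip and the 10-meter walk.

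**Analysis.** SAP 4.7 summarizes observed values, change and percentage change in wall thickness from that baseline: "Descriptive statistics will be provided for actual values, changes, and percentage changes from baseline in echocardiogram parameters (including wall thickness". The study is single-arm (Protocol 4.4), and SAP 3.5 plans no covariate adjustment.

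**The concern.** The subgroup is cut at a threshold on a measurement that contains error, and that same measurement is then the reference for change. Patients whose screening reading happened to be high are kept. Patients whose reading happened to be low fall outside the subgroup and have no further echocardiogram scheduled. The later readings of those who were kept carry no such selection, so their mean drifts down toward the true values without any drug effect.

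The shift is in the direction that would be taken as benefit. It is present in full at the first follow-up echocardiogram and stays at later visits, which is also the pattern of an early, lasting response. Cardiac structure is a stated tertiary objective. With no control and no test, the mean change from baseline is what readers will look at.

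**Working it through.** **Is it one reading or two?** No first-day echocardiogram is scheduled, so SAP 3.4 falls back to the screening value. The averaging rule does not cover echocardiograms, and a parent-study echocardiogram replaces the screening one. As planned, the selecting reading and the baseline reading are the same number.

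**Model.** Observed reading X = true thickness + error, with true thickness ~ N(μ, sb²) and error ~ N(0, se²), errors independent between visits. Let SD = √(sb² + se²) and z = (13 − μ)/SD. With no true change in anyone,

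E[follow-up − baseline | X ≥ 13] = −(se²/SD²) × SD × φ(z)/(1 − Φ(z)).

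**Inputs.** Only the 13 mm cut-off comes from the documents. They give no mean, SD or repeatability for wall thickness and no planned figure to reproduce. The assumptions are μ 12 to 14 mm, sb 2.5 to 3.5 mm and se 0.5 to 1.5 mm.

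**Worked case (μ 13, sb 2.5, se 1.0).** SD = √(6.25 + 1) = 2.693; z = 0; φ(0)/(1 − Φ(0)) = 0.3989/0.5 = 0.798; error share = 1/7.25 = 0.138. Bias = −0.138 × 2.693 × 0.798 = −0.30 mm.

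**Range (mm).**

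| μ | sb | se 0.5 | se 1.0 | se 1.5 |
|---|---|---|---|---|
| 12 | 2.5 | −0.10 | −0.39 | −0.79 |
| 12 | 3.5 | −0.07 | −0.27 | −0.57 |
| 13 | 2.5 | −0.08 | −0.30 | −0.62 |
| 13 | 3.5 | −0.06 | −0.22 | −0.47 |
| 14 | 2.5 | −0.06 | −0.21 | −0.46 |
| 14 | 3.5 | −0.04 | −0.17 | −0.38 |

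Every entry is negative; the size depends mostly on measurement error. Less favorable inputs go further: μ 11, sb 2, se 1.5 gives −1.23 mm.

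**Against sampling noise.** Enrollment is at most 28. With μ 13, half would pass the cut-off, so about 28 × 0.5 = 14 patients. With ρ = sb²/SD², the variance of change in selected patients is (1 − ρ)² × Var(X | X ≥ 13) + sb²(1 − ρ) + se². For sb 2.5:

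| se | SD of change | SE of mean, n = 14 | Bias | Bias / SE |
|---|---|---|---|---|
| 0.5 | 0.70 | 0.19 | −0.08 | 0.4 |
| 1.0 | 1.38 | 0.37 | −0.30 | 0.8 |
| 1.5 | 2.03 | 0.54 | −0.62 | 1.1 |

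**Does a reading not used for selection remove it?** A simulation of 2,000,000 patients (μ 12, sb 2, se 1) gave −0.50 mm when the selecting reading was the baseline (formula −0.49) and −0.002 mm when a separate reading was the reference. In the first case 36% of selected patients showed thinning of at least 1 mm, and 14% showed thickening of at least 1 mm. The Month 6 echocardiogram is such a separate reading.

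**The case against.** The strongest reply is that the size is entirely assumed. With a measurement SD of 0.5 mm the bias is at most 0.10 mm in the grid above. The model also uses one normal distribution with many patients near 13 mm. If the cohort is really a mixture of patients with and without cardiac involvement, fewer may sit near the cut-off and the bias would be smaller. Both points stand and limit the claim about size, though not its direction.

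A reader might infer that the tables will show thinning, or that any thinning seen must be artefact. The documents support neither. The result is a shift in the expected mean, about one standard error or less in a subgroup this small. The protocol's introduction describes relentless disease progression, which would push the other way. An investigator may also repeat tests (Protocol 7.6), and an unscheduled second pre-dose echocardiogram would become baseline under SAP 3.4 and remove the bias for that patient. None is planned.

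It can also be said that SAP 4.7 already reports observed values and lists all echocardiogram data by patient, that nothing in it promises to call thinning a drug effect, and that the analysis is tertiary and descriptive. This is fair and makes the issue one of interpretation, not of error rates. But neither document mentions the selection effect, and reading it out of listings is left to the reader.

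Nor does the point carry over to the cardiac biomarkers: troponin I and NT-proBNP are not selection variables and have their own first-day sample.

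**Conclusion.** The point holds as a bias in expectation. The planned change in wall thickness is measured from the reading that selected the patients, with no control and no scheduled follow-up imaging of unselected patients, so its mean is shifted toward thinning when nothing has changed. Under the stated assumptions the shift is about −0.04 to −0.8 mm. The direction follows from the design; the size is unknown because the documents contain no echocardiographic variability. It is comparable to or smaller than the sampling error of the mean, so true progression or chance could mask it. It concerns how a tertiary descriptive summary is read, and it is worth correcting because the correction is cheap.

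**What to change.** First reconcile the timing. SAP 4.7 places the cardiac assessments at about 3-month intervals, whereas Protocol 6.2.4 and 7.6.14 have echocardiograms about every 6 months and only the biomarkers about every 3 months.

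Then, in SAP 4.7:

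- Keep change from the screening echocardiogram, and state that for wall thickness it is subject to regression to the mean because the same reading selected the subgroup, and that it should not by itself be read as a drug effect.
- Add a supportive summary of wall-thickness change from the Month 6 echocardiogram to Months 12, 18 and 24, noting that Month 6 values played no part in selection.

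The cost is a few lines and one table from echocardiograms already in the protocol schedule. The supportive table omits the first 6 months, so it cannot show an effect that is complete by Month 6, and it omits patients without a Month 6 echocardiogram. For that reason it should stay supportive. A rule that thinning counts as a drug effect only if the Month 6 table agrees would reject a true early effect, and agreement would not establish a drug effect without a control. There is also no need to rank LV strain or the biomarkers as main readouts; that is a matter of preference, and LV strain comes from the same screening examination.
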